### **Adverse events of special interest**

Specific groupings of AESI will be considered and the number of patients with at least one event in each grouping will be reported. Note that certain adverse events may be reported within multiple groupings.

All AESI groupings are defined through the use of Preferred Terms (PT), High Level Terms (HLT), System Organ Classes (SOC), Standardized MedDRA Queries (SMQ), Novartis MedDRA Queries (NMQ) or through a combination of these components. The MedDRA terms to be used are defined in an independent AESI search table which is located in the document management system in the “CREDI Projects/I/ICL670A/Integrated Medical Safety” folder. The latest AESI search table has to be used.

The AESI search table will be used to map reported adverse events to the AESI groupings. The list of adverse events of special interest may be updated during the course of the trial based on accumulating safety data. Therefore clinical study report will list the AE groupings used and provide a listing of the corresponding AESI search table. AESI will be summarized by grouping, preferred term and treatment arm (specifying severity, SAE, relationship, leading to treatment discontinuation, leading to dose adjustment/interruption and requiring additional therapy).

## Laboratory data

Laboratory data from all sources (central and local laboratories) will be combined. All laboratory values will be converted into International System (SI) units.

Raw values as well as absolute and relative change from baseline values for hematology, biochemistry and urinalysis laboratory parameters will be summarized descriptively per time window and treatment arm on the Safety Set 3 and 4 (see [Table 4-2](#) for time windows definition).

Shift tables based on normal ranges to compare baseline to the worst post-baseline value will be provided by parameter and treatment arm for hematology, biochemistry and urinary laboratory data. Same shift table will be provided based on notable/extended ranges for key safety laboratory parameters defined in [Table 2-4](#).

**Table 2-4      Definition of notable/extended ranges for key safety laboratory parameters**

Laboratory parameters	Criteria for notable/extended ranges
Platelet count	< 100 x 10  /L (extended range <50 x 10  /L)
Absolute neutrophils	< 1.5 x 10  /L (extended range <0.5 x 10  /L)
Serum creatinine	> 33% increase from baseline and > ULN at two consecutive measurements at least 7 days apart
Recalculated creatinine clearance	<60 mL/min at two consecutive measurements at least 7 days apart (extended range <40 mL/min at two consecutive measurements at least 7 days apart)
Urinary protein/urinary creatinine ratio	> 1.0 (mg/mg) at two consecutive measurements at least 7 days apart
ALT/AST	>5 x ULN and 2 x baseline (extended range >10 x ULN and >2 x baseline value)

Recalculated creatinine clearance will be calculated using the Schwartz formula (for pediatric population at baseline) described in [Section 3.6.3](#). The Modification of Diet in Renal Disease (MDRD) derivation will be provided in the derived datasets only for possible future requests.

A listing of all laboratory values with values flagged to show the corresponding range classifications relative to the laboratory reference ranges will be provided by laboratory data and treatment arm. Assessment day relative to first dose of study drug will be included and all laboratory assessments collected outside of the on-treatment period will be flagged.

A listing of patients with laboratory abnormalities based on normal ranges and notable/extended ranges will also be provided.

Normal ranges by laboratory parameter will also be provided in a separate listing.

In addition to the above mentioned tables and listings, box plots of absolute value and the absolute change from baseline value for key safety laboratory parameters per time window and treatment arm will be provided as appropriate.

## Vital signs, weight and body mass index

The following criteria define clinically notable abnormalities for vital signs and weight values:

- Clinically notable elevated values
  - Systolic Blood Pressure (BP):  $\geq 180$  mmHg and an increase  $\geq 20$  mmHg from baseline
  - Diastolic BP:  $\geq 105$  mmHg and an increase  $\geq 15$  mmHg from baseline.
  - Pulse rate:  $\geq 120$  bpm with increase from baseline of  $\geq 15$  bpm
  - Weight: increase from baseline of  $\geq 7\%$
- Clinically notable low values
  - Systolic BP:  $\leq 90$  mmHg with decrease from baseline of  $\geq 20$  mmHg
  - Diastolic BP:  $\leq 50$  mmHg with decrease from baseline of  $\geq 15$  mmHg
  - Pulse rate:  $\leq 50$  bpm with decrease from baseline of  $\geq 15$  bpm
  - Weight:  $\geq 7\%$  decrease from baseline

Descriptive statistics will be tabulated per time window and treatment arm using absolute change from baseline values for each vital sign measure, weight and BMI (see [Table 4-2](#) for time windows definition) separately for Safety Set 3 and 4.

All vital sign assessments, weight and BMI will be listed by treatment arm, patient and parameter. In the listings, clinically notable values will also be flagged.

## Cardiac evaluations

Cardiac evaluations include ECG and echocardiogram. Any abnormalities at baseline will be summarized as described in [Section 2.3](#). All findings of patients with new or worsened abnormalities since baseline will be listed separately for Safety Set 3 and Safety Set 4.

## Ocular evaluations

The number of patients with available assessment for each type of ocular evaluation and eye side will be provided by treatment group.

### Visual acuity

Visual acuity will be measured using the Snellen visual acuity. This is determined by establishing the smallest optotypes that can be identified correctly by the patient at a given observation distance. Snellen visual acuity can be reported as a Snellen fraction (m/M) in which the numerator (m) indicates the test distance and the denominator (M) indicates the distance at which the gap of the equivalent Landolt ring subtends 1 minute of arc. For each timepoint, the LogMAR score will be calculated as  $-\log(m/M)$ .

Descriptive statistics of the LogMAR scores at baseline, at each post-baseline visit and changes from baseline at each post-baseline visit will be presented, for each eye by treatment group provided that for a given patient, the assessment was done in the same condition (with/without correction) as done at baseline.

The LogMAR value will be compared at baseline and worst post-baseline based on the identifying clinically meaningful deterioration in LogMAR of  $\leq 0$ ,  $> 0$  to  $< 0.1$ ,  $0.1$  to  $< 0.2$ ,  $0.2$  to  $< 0.3$  and  $\geq 0.3$ , for each eye side by treatment group.

Number and percentage of patients with clinically relevant LogMAR change from baseline more or equal than 0.2 and more or equal than 0.3 will be summarized by treatment arm. For patients with such values, a listing will also be provided.

### **Slit lamp**

For each considered evaluation type and eye, the number of patients with and without abnormality (normal, insignificant, significant and any) will be provided by treatment arm. In addition, a shift table will present any changes in interpretation compared to baseline. A listing of patients with any abnormality will be provided.

### **Tonometry**

Descriptive statistics of the intraocular pressure at baseline, at each post-baseline visit and changes from baseline at each post-baseline visit will be presented, by eye and treatment group.

The number of patients with clinically relevant changes from baseline intraocular pressure above 5 mmHg and 10 mmHg will be summarized by treatment arm. For patients with such values, a listing will also be provided.

Intraocular pressure will also be summarized in shift table (baseline and worst post baseline value) for each eye side considering the following categories:  $< 22$ ,  $\geq 22$  and  $< 30$  and  $\geq 30$  mmHg.

### **Fundus oculi**

For each eye, the number of patients with and without abnormality (normal, insignificant, significant and any) will be provided by treatment arm. In addition, shift table will be done to present any changes in interpretation compared to baseline. A listing of patients with any abnormality will be provided.

### **Growth and Development**

**Growth velocity** will be listed at baseline and core EOT visit and summarized using descriptive statistics by sex and age group during the core phase for the Safety Set 3. Summaries and listing will be repeated for the entire granule period on the Safety Set 4.

The growth velocity in height which evaluates the rate of growth per year will be calculated on the difference with the previous measure of height (in cm) and the time period (in days) as:

Growth velocity (cm / year) =

$$\frac{(height V_x - height V_{x-1}) * F}{date V_x - date V_{x-1}}$$

(with  $V_x$  = actual visit ;  $V_{x-1}$  = previous visit ;  $F = 365.25$ ).

**Pubertal stage** assesses the stage of physical development of sex characteristics. The characteristics breast development, pubic hair, testes and penis size are evaluated based on the Tanner scale: for each characteristic there are 5 classes (Tanner stage 1 to 5) indicating the level of development of that specific characteristic.

The age will be summarized descriptively at baseline and core EOT visit for the core phase by sex, characteristic, Tanner stage and treatment arm. For the entire granule period, the same summary will be repeated at baseline and at each annual assessment.

**A listing will be provided** including the Tanner stage as well as the individual records for each sex characteristic by visit.

### Other safety data

All data from auditory evaluation, hepatitis testing, and pregnancy test will be listed.

Patients with clinically significant abnormal interpretations or abnormal values will be flagged as well as positive pregnancy test results.

Data related to blood transfusion during treatment phase will be listed by treatment arm.

### 2.9.3 Pharmacokinetics parameters

#### 2.9.3.1 General considerations

Pharmacokinetic (PK) analyses will be based on PK parameters derived by Non-Compartmental Analyses (NCA) and Compartmental Analyses (CA) ([Table 2-5](#)) and on PK concentrations. PK concentrations and Parameters are based on serum Exjade concentrations.

**Table 2-5 Pharmacokinetic Parameters (NCA and CA)**

NCA Parameters	
AUClast	The AUC from time zero to the last measurable concentration sampling time (tlast) (mass x time x volume  )
AUCinf	The area under the plasma concentration-time curve extrapolated to infinity (mass x time x volume  )
AUCtau	The AUC calculated to the end of a dosing interval (tau) at steady-state (mass x time x volume  )
Cmax	The maximum (peak) observed plasma, blood, serum, or other body fluid drug concentration (mass x volume  )
Tmax	The time to reach maximum (peak) plasma drug concentration after dose administration (time)
R	Accumulation index calculated as (AUC0-24h at steady state)/(AUC0-24h after the first dose)
CA Parameters	
ka	absorption rate constant (hr  )
CL/F	apparent clearance for ICL670 and where F is the bioavailability (L/h)
V1/F	apparent volume of the central compartment for ICL670 (L)
Q/F	apparent distributional clearance for ICL670 (L/h)
V2/F	apparent peripheral volume for ICL670 (L)

Note: PK parameters are defined assuming a two compartment disposition model with first order absorption. In the unexpected case, the structure of the compartmental model require a change (e.g. for concentrations after granule application) PK parameter may change.

The daily dose categories defined in [Table 2-6](#) will be used.

The PAS-1 will be used for the analysis of PK concentrations and characterization of Cmin and Cmax. The PAS-2 will be used to summarize PK parameters and visualize PK profiles. PK/safety analyses will be based on the Safety Set 3 and PK/efficacy analyses on the FAS-3 patients who also belonged to the PAS-1.

Descriptive statistics of dose-adjusted PK concentration by visit and time point and PK parameters by visit will include arithmetic and geometric means, median, SD, CV%, CV% of the geometric mean, minimum and maximum. Zero concentrations will not be included in the geometric mean calculation.

Coefficient of variation CV (%) is calculated as follows:  $100 * (\text{SD}/\text{arithmetic mean})$ . Geometric CV (%) is calculated as follows:  $\text{CV}(\%) = 100 \sqrt{(\exp(\sigma^2) - 1)}$  where  $\sigma^2$  denotes the variance of the log-transformed values.

Unscheduled samples will not be included in the descriptive analysis by time point but these samples will be flagged in the corresponding concentration listing.

Missing concentrations will not be imputed. Concentrations below the Lower Limit of Quantification (LLOQ) will be labeled as such in the concentration data listings.

Concentrations below the limit of quantitation will be treated as zero in summary statistics and excluded from geometric mean and geometric Coefficient of Variation (CV%) computation.

All individual data will be listed on the FAS-3 and those excluded from the analysis will be flagged.

### **2.9.3.2 Evaluation of pre-dose PK data to support the assessment of compliance**

Pre-dose (Cmin) PK data from patients in the PAS-1 will be analyzed to assess variability of individual patient's compliance. The following approach will be used:

A linear mixed effect power model to pre-dose samples which fulfill compliance criteria in terms of steady state (4 consecutive same doses prior to the PK drawn), time-windows (PK sample drawn 20 to 28 hours after previous dose) and without any vomiting episodes within the 4 hours prior to the PK sample will be fitted. The model will consider dose, treatment group, stratification factors and potential other factors, such as body weight as covariates.

Predicted pre-dose concentrations will be compared with observed pre-dose concentrations considering all patients and pre-dose samples in PAS-1. Distributions of the difference between predicted and observed Cmin values will be shown graphically by boxplots for both treatment groups and visit.

### 2.9.3.3 Pharmacokinetics analyses

Dose-adjusted PK concentrations will be summarized by treatment, visit and time point based on PAS-1. The individual dose-adjusted pre-dose concentration will be plotted for Week 1, Week 3, Week 5, Week 9, Week 13, Week 17, Week 21, Week 25, Week 29, Week 33, Week, 37, Week 41 and Week 45 based on data from all patients. In addition arithmetic mean dose-adjusted pre-dose concentration will be plotted over time by treatment. These analyses will be based on the PAS-1.

Dose- adjusted PK parameters will be summarized by treatment for Week 1 and Week 5based on PAS-2. In addition, dose-adjusted PK concentrations will be summarized by treatment and time point for Week 1 and Week 5 on the PAS-2. Dose-adjusted individual concentration-time profiles will be plotted for Week 1 and Week 5. These analyses will be based on the PAS-2.

The dose-adjusted PK concentration and dose-adjusted PK parameter will be calculated as follows:

- For patients taking deferasirox DT:  
Dose-adjusted PK concentration or parameter = (PK concentration or parameter/actual dose)\*20
- For patients taking deferasirox granules:  
Dose-adjusted PK concentration or parameter = (PK concentration or parameter/actual dose)\*14

### 2.9.3.4 Exploration of PK/PD relationship

To characterize the exposure-efficacy relationship, serum ferritin change from baseline will be fitted by a linear mixed effect model with log- transformed matching pre-dose concentrations and post-dose concentrations as covariates and subject as random effect.

To characterize the exposure-safety relationship: Serum creatinine change from baseline, creatinine clearance change from baseline and urine protein creatinine ratio change from baseline will be fitted by a linear mixed effect model with log-transformed matching pre-dose and post-dose concentrations as covariates and subject as random effect. A model on post-baseline measurement and adjusted by corresponding baseline as covariate might be considered if improves the model fit.

Incidence of notable serum creatinine and incidence of notable serum creatinine clearance events will be analyzed by a logistic regression fitted by GEE methods as appropriate including log-transformed pre- and post-dose concentrations (see [Table 2-4](#) for notable range definition). These analyses will be conducted if notable events were reported for a minimum of 20 patients. If notable events were reported for less than 20 patients a descriptive approach will be followed.

For all statistical models other covariates such as demographic characteristics may be included if appropriate (e.g. underlying disease).

PK/PD listing will be provided.

All PK/safety and PK/efficacy analyses will be based on the Safety Set 3 and on the FAS-3, respectively.

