### **7.2.2 Serum Ferritin**

Serum ferritin test will be performed during the core phase at Screening Visits 1 and 2 (in the absence of infection) to assess the eligibility of the patient. The baseline serum ferritin value is defined as the average of the two measurements obtained during the screening period. Thereafter serum ferritin testing will be performed at weeks 5, 9, 13, 17, 21, 25, 29, 33, 37, 41, 45 and EOT(core)/777 visits to evaluate the clinical benefit related to improved compliance of the new formulation. This will be done monthly as per Exjade prescribing information during

the extension phase. A central laboratory will be used for analysis of all specimens collected.  

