#### **10.5.6.3 To explore PK/PD relationship**

Serum ferritin change from baseline will be fitted by a linear mixed effect model with log-transformed matching pre-dose concentrations as covariates and subject as random effect.

Serum creatinine change from baseline, serum creatinine clearance change from baseline and urine protein creatinine ratio change from baseline will be fitted by a linear mixed effect model with log-transformed matching pre-dose and post-dose concentrations respectively as covariates and subject as random effect.

Incidence of notable serum creatinine events as defined in [Table 10-1](#) will be analyzed by a logistic regression fitted by GEE methods as appropriate including matching log-transformed pre- and post-dose concentrations, respectively.

Incidence of notable serum creatinine clearance events as defined in [Table 10-1](#) will be analyzed by a logistic regression fitted by GEE as appropriate methods including matching log-transformed pre- and post-dose concentrations, respectively.

For all statistical models other covariates such as demographic characteristics may be included if appropriate.

Other non-linear mixed effect models, such as effect-compartment models, may be established if appropriate to further explore exposure efficacy or safety relationship and will be reported separately.

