To evaluate compliance using a daily PRO/ObsRO questionnaire	Rate of dosing instructions deviations (doses missed / not taken at the same time every day)	Refer to Protocol Section 10.5.4 / SAP Section 2.9.1
To evaluate pre-dose PK data to support the assessment of compliance	Pre-dose deferasirox concentrations in all patients [except Egypt] at weeks 1, 3, 5, 9, 13, 17, 21, 25, 29, 33, 37, 41 and 45 (13 samples)	Refer to Protocol Section 10.5.5.1 / SAP Section 2.9.3
Post-dose data to be analyzed along with pre-dose PK data	Post-dose deferasirox concentrations between 2 and 4 hours post-dose at Weeks 5 and 9 (2 samples)	Refer to Protocol Section 10.5.5.2 / SAP Section 2.9.3
To explore exposure-response relationships for measures of safety and effectiveness	Serum creatinine change from baseline, notable serum creatinine events, serum creatinine clearance change from baseline and notable serum creatinine clearance events,	Refer to Protocol Section 10.5.5.3 / SAP Section 2.9.3

Objective	Endpoint	Analysis
	urine protein creatinine ratio change from baseline and serum ferritin change from baseline, in relationship to pre- and post-dose deferasirox concentrations.	
Secondary (Optional Extension phase) To assess additional safety data about new formulation (granules) in pediatric population	Overall safety, as measured by frequency and severity of adverse events (including active monitoring for renal toxicity; including renal failure, hepatic toxicity; including hepatic failure, and gastrointestinal hemorrhage), and changes in laboratory values from baseline (serum creatinine, creatinine clearance, ALT, AST, RBC and WBC). In addition, vital signs, physical, ophthalmological, audiometric, and growth and development evaluations will be assessed.	Protocol sections 10.5.3 and 10.6.1 / SAP Section 2.9.2

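### As worded, the SAP's exposure-response mixed models combine pre-dose and post-dose concentrations, which limits them to weeks 5 and 9 and omits the 24-week time point

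*SAP*

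**What the plan says.** **Protocol.** Section 10.5.6.3 fits ferritin change on "log-transformed matching pre-dose concentrations as covariates and subject as random effect". For serum creatinine, creatinine clearance and UPCR it uses "log-transformed matching pre-dose and post-dose concentrations respectively as covariates". The objectives table (protocol Table 3-1) is broader: it lists ferritin change, along with the renal outcomes, in relation to both pre-dose and post-dose concentrations.

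**SAP (Amendment 3).** Section 2.9.3.4 gives the ferritin model log- "transformed matching pre-dose concentrations and post-dose concentrations as covariates and subject as random effect". The three continuous renal outcomes get "log-transformed matching pre-dose and post-dose concentrations as covariates and subject as random effect", without *respectively*. The GEE logistic models for notable renal events are described as "including log-transformed pre- and post-dose concentrations". They are run only if at least 20 patients have notable events; otherwise the approach is descriptive. SAP Table 3-1, the list of changes to protocol-specified analyses, reads NA.

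**Sampling.** SAP Table 1-1 schedules "Post-dose deferasirox concentrations between 2 and 4 hours post-dose at Weeks 5 and 9 (2 samples", whereas pre-dose samples are taken "at weeks 1, 3, 5, 9, 13, 17, 21, 25, 29, 33, 37, 41 and 45 (13 samples". Protocol section 7.2.2 sets the ferritin schedule: "Thereafter serum ferritin testing will be performed at weeks 5, 9, 13, 17, 21, 25, 29, 33, 37, 41, 45 and EOT(core)/777 visits".

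**Handling.** SAP section 2.9.3.1 does not impute missing concentrations. Section 4.6.2.2 names PROC MIXED for the linear models and PROC GENMOD for the logistic ones.

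**The concern.** If pre-dose and post-dose concentrations sit in the same model, a record is usable only when both are present. PROC MIXED leaves out any record with a missing covariate, so every visit with a trough but no post-dose draw is lost. The trial draws troughs from children at 13 visits so that exposure can be followed over the core phase. A joint model would set most of them aside and describe only the first two months.

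The early cut-off matters most for pre-treated patients, who may be up to 120 of the 216 in FAS-3. Their ferritin-based dose adjustment is scheduled every 3 months (protocol section 6.1.1), after the last usable record. The 24-week and 48-week ferritin time points would lie outside the model for everyone.

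**Working it through.** **1. Check that the sampling schedule is read correctly.** 13 pre-dose + 2 post-dose = 15 samples. At 2 mL each, 15 × 2 = 30 mL, which is the total in protocol Table 7-5.

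**2. Outcome visits after baseline.**
- Ferritin (protocol 7.2.2): weeks 5, 9, 13, 17, 21, 25, 29, 33, 37, 41 and 45, which is 11 visits, plus end of treatment. No PK sample is scheduled at end of treatment.
- Creatinine and creatinine clearance (protocol 7.2.4.6.2): weeks 2 and 3, then weeks 5 to 45 as above, plus end of treatment. UPCR is measured at every visit (7.2.4.6.3).

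**3. Match outcome visits to concentrations.**

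| Outcome | Visits with a trough | Visits with both samples | Kept | Lost |
|---|---|---|---|---|
| Ferritin | 11 (weeks 5 to 45) | 2 (weeks 5, 9) | 2/11 = 18% | 9/11 = 82% |
| Creatinine, clearance, UPCR | 12 (weeks 3 and 5 to 45) | 2 (weeks 5, 9) | 2/12 = 17% | 10/12 = 83% |

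**4. Convert visits to weeks of treatment.** SAP Table 4-2 puts the planned visit at study day (5 + 4k − 1) × 7 + 1. Weeks of treatment completed are (study day − 1)/7.
- Week 9 (k = 1): day 57, and 56/7 = 8 weeks.
- Week 25 (k = 5): day 169, and 168/7 = 24 weeks.
- Week 45 (k = 10): day 309, and 308/7 = 44 weeks.

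The joint ferritin model therefore stops at 8 weeks, while a pre-dose-only model reaches 44 weeks.

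**5. Confirm the mechanics.** In an illustrative mixed-model fit to 200 simulated patients with complete scheduled sampling, the pre-dose model used 200 × 11 = 2200 records. The joint model used 200 × 2 = 400, none later than week 9. The simulated effects were assumed, so only the record counts are relied on.

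**6. After separating the models.** The pre-dose model has 11 ferritin visits or 12 renal visits. The post-dose model has 2 visits for each outcome.

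**The case against.** The strongest reply is that section 2.9.3.4 never says the two concentrations are fitted jointly. The singular model in the renal sentence covers three different outcomes, so the singular proves nothing. SAP section 2.1 says the data are analysed according to section 10 of the protocol. Table 3-1 lists no departures, and the document history says the PK analyses were updated to align with the protocol. Section 4.6.2.2 leaves further model detail to CSR Appendix 16.1.9, which is not available here. On this account the intent was separate models and *respectively* was lost in drafting.

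That may be the intent, and it is why the point is about wording rather than about what was fitted. It does not remove the problem. The text names both concentrations as covariates, and the same section uses *respectively* where it assigns the analysis sets. A programmer following it literally would fit them together.

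A second reply is that post-dose exposure in the ferritin analysis is not the SAP's invention, since protocol Table 3-1 lists it. This stands. The protocol's table and its section 10.5.6.3 disagree, and a pre-dose-only correction would drop a listed relationship.

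A reader might also infer several stronger claims that the documents do not support:
- *Later renal events drop out of the GEE models.* The SAP does not say *matching* there, so a visit-by-visit loss is not explicit.
- *All data after dose increases are lost.* ICT-naïve patients may be adjusted after 4 weeks (protocol 6.1.1), so week 9 can follow an increase.
- *Collinearity makes the coefficients uninterpretable.* Some correlation between the two concentrations is plausible, but the documents give no figure for it.
- *The joint model must have been used.* The End of Core Phase and final SAPs decline to repeat the exposure-efficacy analysis, saying no further data were collected after the primary cut-off of 31-May-2018. The Amendment 6 rationale says all patients had completed the core phase by 18-Dec-2018. That fits a model ending at week 9, but does not prove one was fitted.

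**Conclusion.** The point holds as a defect in the written specification. Followed literally, SAP section 2.9.3.4 keeps 18% of trough-matched ferritin visits and 17% of trough-matched renal visits, with nothing after 8 weeks of treatment. The departure from protocol section 10.5.6.3 is undeclared.

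The counts assume complete attendance at scheduled visits, no imputation (as the SAP states) and exclusion of records with a missing covariate. A missed post-dose draw would remove a further visit. Week 1 and week 5 profiles from patients enrolled under the original protocol add no ferritin visit to the count, because week 1 has no post-baseline ferritin. Unscheduled PK samples could add isolated records.

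A reader might conclude that the exposure-response objective cannot be answered. The documents do not support that: the SAP allows some flexibility in model form, the protocol allows further non-linear mixed effect models, and the troughs needed are already scheduled. The severity is moderate. This is an exploratory secondary analysis, and the co-primary tests, their error rate and the sample size are unaffected.

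**What to change.** In SAP section 2.9.3.4, state that pre-dose and post-dose concentrations are fitted in separate models for each outcome:
- **Pre-dose model:** all matched visits, meaning weeks 5 to 45 for ferritin and weeks 3 to 45 for creatinine, clearance and UPCR.
- **Post-dose model:** weeks 5 and 9 only, labelled as an early-treatment analysis.
- **Ferritin:** make the pre-dose model the main one and add the separate post-dose model. This reconciles protocol section 10.5.6.3 with protocol Table 3-1.
- **GEE logistic models:** apply the same separation if the 20-patient condition is met, and say whether concentrations are matched by visit.

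If a joint model is really wanted, declare it in SAP Table 3-1 with a rationale and state how visits without a post-dose sample are handled.

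The cost is a few sentences and a changed model statement, with no new data. If reported results came from a joint model, they can be re-run on the existing data.
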